## 11.2 Clinical Laboratory Variables

Descriptive statistics for clinical laboratory values (in SI units) and changes from baseline to Week 4/ET as well as shift tables from baseline to Week 4/ET for quantitative variables will be presented for the following clinical laboratory variables.

**Hematology** Hemoglobin, hematocrit, red blood cells, platelet count, white blood cell count – total and differential, total neutrophils (absolute and relative), eosinophils (absolute and relative), monocytes (absolute and relative), basophils (absolute and relative), and lymphocytes (absolute and relative).

**Biochemistry** Sodium, potassium, glucose, blood urea nitrogen, creatinine, calcium, chloride, thyroid-stimulating hormone, thyroxine, tri-iodothyronine, phosphorus, total protein, total CO2 (bicarbonate), albumin, aspartate transaminase, alanine transaminase, gamma glutamyl transferase, alkaline phosphatase, total bilirubin, and uric acid.

**Urinalysis** pH, glucose, protein, blood, ketones, bilirubin, nitrites, leukocyte esterase, and specific gravity.

Microscopic examination will be conducted if protein and/or blood is/are detected during urinalysis. At a minimum the microscopic examination will consist of red blood cells, white blood cells, casts, and bacteria.

Clinical laboratory test values are potentially clinically important (PCI) if they meet either the low or high PCI criteria listed in [Table 5](#). The number and percentage of subjects with post-baseline PCI values will be tabulated. The percentages will be calculated relative to the number of subjects with available baseline values and at least 1 post-baseline assessment. The numerator is the total number of subjects with at least 1 post-baseline PCI value. A supportive listing of subjects with post-baseline PCI values will be provided including the subject number, baseline, and post-baseline values.

**Table 5: Criteria for Potentially Clinically Important Laboratory Tests**

Parameter	SI Unit	Lower Limit	Higher Limit
Biochemistry			
Albumin	g/L	< 30g/L	-
Alkaline phosphatase			$\geq 2.5 \times \text{ULN}$
Aspartate transaminase	-	-	$\geq 3 \times \text{ULN}$
Alanine transaminase	-	-	$\geq 3 \times \text{ULN}$
Blood urea nitrogen	mmol/L	-	$> 10.71 \text{ mmol/L or } > 2.5 \times \text{ULN}$
Calcium, total	mmol/L	2	2.88
Creatinine	$\mu\text{mol/L}$	-	$> 176.80 \mu\text{mol/L or } > 1.5 \times \text{ULN}$
Gamma glutamyl transferase	-	-	$\geq 2.5 \times \text{ULN}$
Glucose	mmol/L	< 3.05	> 8.88
Phosphorus, inorganic	mmol/L	< 0.81	2.26
Potassium	mmol/L	< 3.0	> 5.5
Thyroid stimulating hormone	-	< LLN	$> 2 \times \text{ULN}$
Sodium	mmol/L	< 130	> 150
Uric acid	$\mu\text{mol/L}$	-	> 594.85
Bilirubin, total	$\mu\text{mol/L}$	-	> 34.21
Protein, total	g/L	< 50	> 90
Hematology			
Basophils	-	-	> 10%
Hemoglobin	g/L	90	160
Hematocrit	%	< 30%	> 50%
Platelet count	$10^9/\text{L}$	75	600
Red blood cells	$\text{X } 10^{12}/\text{L}$	2.5	7.5
White blood cell count	$\text{X } 10^9/\text{L}$	< 3.0	> 16.0
Neutrophils	$\text{X } 10^9/\text{L OR } \%$	$< 1 \times 10^9/\text{L OR } < 30\%$	$> 6.2 \times 10^9/\text{L OR } > 70\%$
Eosinophils	$10^9/\text{L OR } \%$	NA	$0.5 \times 10^9/\text{L OR } > 10\%$
Lymphocytes	%	< 10%	> 70%
Monocytes	%	-	> 20%
URINALYSIS			
Glucose	-	-	Positive Value (excluding trace)
Protein	-	-	Positive Value (excluding trace)
Blood	-	-	Positive Value (excluding trace)

**Table 5: Criteria for Potentially Clinically Important Laboratory Tests**

Parameter	SI Unit	Lower Limit	Higher Limit
Ketones	-	-	Positive Value (excluding trace)
Bilirubin	-	-	Positive Value (excluding trace)
Leukocyte esterase	-	-	Positive Value (excluding trace)
Nitrites	-	-	Positive Value (excluding trace)

LLN: Lower limit of normal value provided by the laboratory

ULN: Upper limit of normal value provided by the laboratory

All clinical laboratory data will be listed for the safety set.

**Table 6: Criteria for Potentially Clinically Significant Vital Signs**

Vital Sign Parameter	Flag	Criteria a	
		Observed Value	Change from Baseline
Sitting Systolic blood pressure (mmHg)	High	≥120	Increase of >10
	Low	<75	Decrease of >10
Sitting Diastolic blood pressure (mmHg)	High	≥85	Increase of >10
	Low	<40	Decrease of >10
Pulse rate (beats per minute)	High	≥130	Increase of >15
	Low	≤55	Decrease of >15
Weight (kg)	High	-	Increase of ≥7%
	Low	-	Decrease of ≥7%
Temperature (deg. C)	High	>39	-
	Low	<35	-
BMI (kg/m  )	High	>95th percentile for age and sex	-
	Low	<5th percentile for age and sex	-

a A post-baseline value is considered as a PCI value if its meets either the criteria for observed value or the criteria for change from baseline.

Measurements of oral or tympanic temperature, sitting respiratory rate will be performed at the screening visit and ET visit only.

Pulse rate (beats per minute) will be considered abnormal if a value is lower than the 1st percentile or higher than the 99th percentile cut-off values listed in [Table 7](#).

**Table 7: Normal Range of Pulse Rate (beats/min)**

	1st Percentile	99th Percentile
Males, 4-5 years	69	120
Females, 4-5 years	70	132

Source: National health statistics report: Resting Pulse Rate Reference Data for Children, Adolescents, and Adults: United States, 1999–2008

<https://www.cdc.gov/nchs/data/nhsr/nhsr041.pdf>

The number and percentage of subjects with abnormal pulse rate values for at least 1 post-baseline assessment will be tabulated for the lower than the 1st percentile and higher than the 99th percentile cut-off values, respectively, for males and females separately. The denominator will be the number of subjects in the safety set (per sex) with at least 1 post-baseline pulse measurement. The numerator is the total number of subjects with at least 1 abnormal pulse record. A supportive listing of subjects with abnormal pulse rate values will be provided.

In addition, following the US Department of Health and Human Services standards, blood pressure values higher than the 95th percentile determined by sex, age, and height percentiles will be considered abnormal. The cut-off values are presented in [Table 8](#).

**Table 8: 95th Percentile Cut-off Values of Blood Pressure Norms by Sex, Age, and Height Percentiles**

Age (y)	Systolic Blood Pressure (mmHg)							Diastolic Blood Pressure (mmHg)							
	Percentile of Height							Percentile of Height							
Boys															
	5%	10%	25%	50%	75%	90%	95%		5%	10%	25%	50%	75%	90%	95%
4	106	107	109	111	112	114	115		66	67	68	69	70	71	71
5	108	109	110	112	114	115	116		69	70	71	72	73	74	74
Girls															
4	105	106	107	108	110	111	112		68	68	69	70	71	71	72
5	107	107	108	110	111	112	113		70	71	71	72	73	73	74

Source: National Heart Lung and Blood Institute; May 2004

[http://www.nhlbi.nih.gov/guidelines/hypertension/child\\_tbl.htm](http://www.nhlbi.nih.gov/guidelines/hypertension/child_tbl.htm)

The number and percentage of subjects with any post-baseline blood pressure values higher than the 95th percentile (exclusive) will be tabulated by sex. The denominator will be the number of subjects in the safety set (per sex) with at least 1 post-baseline blood pressure measurement. The numerator will be the total number of subjects with at least 1 blood pressure value higher than the 95th percentile. A supportive listing of all subjects with abnormal blood pressure values will be provided.

All vital signs data will be listed for the safety set.

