3.2 Duration and Study Completion Definition

Each subject's maximum duration of participation is expected to be approximately 9 weeks. The study will be completed in approximately 12 months.

- Screening period:
 - A maximum of 32 days before the first dose of investigational product
 - If applicable, this includes a washout period that is to start 7 days before the first dose of investigational product.
- Treatment Period: Total duration for the treatment period is approximately 30 days for subjects in the rich PK sampling portion of the study and 29 days for subjects in the sparse PK sampling portion of the study.
- Follow-up contact: At the last clinic visit, subjects and their parent/legally authorized representative (LAR) will be offered to rollover into the SHP465-308 study. If subjects agree and their parent/LAR signs the informed consent form, this will end their participation in the SHP465-112 study. If they do not want to participate in the SHP465-308 study, follow-up contact will be conducted approximately 1 week (7 days [± 2 days]) following the last dose of investigational product.

The Study Completion Date is defined as the date the final subject, across all sites, completes their final protocol-defined assessment. Please note that this includes the follow-up visit or contact, whichever is later. The Study Completion Date is used to ascertain timing for study results posting and reporting.

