4.1 Inclusion Criteria

The subject will not be considered eligible for the study without meeting all of the following criteria (including test results):

1. Subject is a male or female aged 4 years to 5 years inclusive at the time of consent.
2. Subject and parent/LAR are willing and able to fully comply with all of the testing and requirements defined in the protocol. Specifically, the parent/LAR must be available at approximately 8:00 AM (± 1 hour) to administer the dose of investigational product at the time points specified in the protocol.
3. Subject's parent/LAR must sign the informed consent form, and there must be documentation of assent (if applicable) by the subject in accordance with the International Council for Harmonisation (ICH) Good Clinical Practice (CGP) Guideline E6 (2016) and any updates, and applicable regulations, before starting any study-related procedures.
4. Subject satisfies the following ADHD criteria during the screening period:
 - Meets the Diagnostic and Statistical Manual of Mental Disorders, Fifth Edition (DSM-5) criteria for a primary diagnosis of ADHD (any subtype) based on a detailed psychiatric evaluation using the Mini International Neuropsychiatric Interview for Children and Adolescents (MINI-KID)
 - Has an ADHD Rating Scale-5 (ADHD-RS-5) Child, Home Version Total Score of ≥ 28 for boys and ≥ 24 for girls
 - Has a Clinical Global Impressions-Severity of Illness (CGI-S) score ≥ 4 .
5. Subject functions at an age-appropriate level intellectually, as determined by the investigator.
6. Subject has undergone an adequate course of nonpharmacological treatment **OR** the subject has a severe enough condition to consider enrollment without undergoing prior nonpharmacological treatment, based on the investigator's judgment **OR** has never taken ADHD medication **OR** has taken ADHD medication with unacceptable efficacy and/or tolerability.
7. Subject has the ability to take investigational product by either swallowing the capsule whole or sprinkling the capsule contents in applesauce and ingesting the entire mixture immediately without chewing.
8. Subject has lived with the same parent/LAR for at least 6 months.

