7.1.1 Screening and Washout Period

Subjects will be screened within 32 days prior to initiation of dosing of the investigational product. During the screening period, the eligibility of subjects will be assessed. All screening assessments and procedures are to be performed by the principal investigator or a qualified designee. A complete list of screening procedures to be performed is provided in [Table 1](#) for the rich PK sample subset and [Table 2](#) for the sparse PK sample subset.

The principal investigator or his/her designee must obtain written informed consent and assent from the subject's parent/LAR prior to any study-related procedures conducted during the screening period. There must also be documentation of assent (if required by the institutional review board [IRB]), indicating that the subject is aware of the investigational nature of the study and the required procedures and restrictions, prior to the performance of any study-related procedures.

If subjects are currently taking ADHD medication, they are to discontinue their current ADHD medication at least 7 days prior to the first dose of investigational product (please refer to Section [4.2](#) for additional information).

Screening procedures may take place across multiple days to allow enough time to complete all procedures and confirm initial subject eligibility. Screening procedures and dates should be well documented in the source documents. The date of the screening visit is the date the parent/LAR has signed informed consent for this study.

A screen failure is a subject who has given informed consent and failed to meet any of the inclusion and/or met at least 1 of the exclusion criteria and has not been enrolled or administered investigational product(s).

Subjects cannot be rescreened once they have been designated as a definite screen failure. Reassessment of subjects who failed specific inclusion/exclusion criteria is not allowed.

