APPENDIX 2.3 BLOOD PRESSURE LEVELS FOR BOYS BY AGE AND HEIGHT PERCENTILE

To determine the eligibility of a male subject for entry in the study (based on the study inclusion criteria), first determine the percentile of height for the subject based on their age (as a whole number based on the subject's last birthday; [Appendix 2.2](#)). For subjects who fall between the 2 height percentiles, use the lower of the 2 percentiles. Once the subject's age and height percentile for age are determined, use the following table to determine eligibility.

All blood pressure values listed as follows are 95th percentile for age and height percentile. The subject's systolic and diastolic blood pressure readings at the screening visit and the baseline visit (predose on Day 1) must not exceed the following corresponding table value for their age and height percentile.

Age (Year)	Systolic Blood Pressure (mmHg)							Diastolic Blood Pressure (mmHg)						
	← Percentile of Height →							← Percentile of Height →						
	5%	10%	25%	50%	75%	90%	95%	5%	10%	25%	50%	75%	90%	95%
4	106	107	109	111	112	114	115	66	67	68	69	70	71	71
5	108	109	110	112	114	115	116	60	70	71	72	73	74	74
6	109	110	112	114	115	117	117	72	72	73	74	75	76	76

Source: National Heart Lung and Blood Institute; May 2004

http://www.nhlbi.nih.gov/guidelines/hypertension/child_tbl.htm

[figure not shown]

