## 2. STUDY DESIGN

### 2.1 General Study Design

The study will be a Phase 1, open-label, multiple-dose, PK, safety, and tolerability study in children aged 4 to 5 years diagnosed with attention-deficit/ hyperactivity disorder (ADHD). Enrollment will be stratified by sex to ensure that at least 2 of the 10 subjects expected to complete the rich PK sampling portion of the study and at least 3 of the 10 subjects expected to complete the sparse PK sampling portion of the study are females.

Following the screening visit, eligible subjects will return to the clinical research center (CRC) on Day 1 of Week 1 to reconfirm eligibility criteria and enter into the treatment phase. Total duration for the treatment period is approximately 30 days for subjects in the rich PK sampling portion of the study and 29 days for subjects in the sparse PK sampling portion of the study. In the study, single 6.25 mg dose of SHP465 will be administered daily for 28 days ( $\pm 1$  day) at 8:00 AM ( $\pm 1$  hour).

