**Table 3: Estimates of Clearance and Volume of Distribution for *d*-Amphetamine and *l*-Amphetamine**

	SHP465 12.5 mg Children (6 to 12 years)		SHP465 25 mg Adolescents (13 to 17 years)	
CV (%)	CL/F (L/h)	Vz/F (L)	CL/F (L/h)	Vz/F (L)
d -amphetamine	25.0	28.5	23.7	18.4
l -amphetamine	26.9	32.2	28.4	22.0

CL/F=body clearance; CV=coefficient of variation; Vz/F=volume of distribution

Source: SHP465-111 Clinical Study Report (06 May 2016) Tables 9-1 and 9-4.

The sample size estimates use the within-subject *l*-amphetamine variability of 32.2%, since it is numerically bigger. Applying the methods from the manuscript by Wang et al. ([2012](#)), sample size estimations with related probability for corresponding coefficients of variation are provided as follows:

CV (%)	Number of Subjects Required	Probability of the Point Estimate Within the Prespecified Interval (%)
18.4	5	89
22.0	5	80
23.7	6	88
25.0	6	82
26.9	7	89
28.4	7	88
28.5	7	88
32.2	8	90

CV=coefficient of variation

Based on these data, the PK sampling analysis will need at least 8 subjects in total to provide reliable PK results.

Approximately 24 subjects are expected to be enrolled to ensure that 10 subjects will complete the rich PK sampling portion of the study and an additional 10 subjects will complete the sparse PK sampling portion of the study. Enrollment will be stratified by sex to ensure that at least 2 of the 10 subjects in the rich PK sampling portion of the study and at least 3 of the 10 subjects in the sparse PK sampling portion of the study expected to complete the study are females.

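### SAP Table 8 stops at age 5 and SAP 11.3 does not say which age selects the row, so readings after a sixth birthday may be misclassified in one descriptive table

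*SAP*

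**What the plan says.** Age is fixed at entry. Protocol 4.1, criterion 1: "Subject is a male or female aged 4 years to 5 years inclusive at the time of consent". Protocol 7.1.1 ties screening to consent: "The date of the screening visit is the date the parent/LAR has signed informed consent for this study". Protocol 3.2 gives the length of screening: "A maximum of 32 days before the first dose of investigational product". SAP 2.1 gives the time on study: "Total duration for the treatment period is approximately 30 days for subjects in the rich PK sampling portion of the study and 29 days" for the sparse subset. SAP 11 analyses assessments taken up to 2 days after the last dose, so the rich subset's final visit on Day 9 of Week 4 is included.

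For blood pressure, SAP 11.3 states that "blood pressure values higher than the 95th percentile determined by sex, age, and height percentiles will be considered abnormal". It then tabulates, by sex, children with any post-baseline value above the limit. The denominator is every child with a post-baseline measurement. The limits are in Table 8 ("95th Percentile Cut-off Values of Blood Pressure Norms by Sex, Age, and Height Percentiles"), which has rows for ages 4 and 5.

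The SAP uses age in two ways. SAP 7.1 gives the general definition: whole years at consent. SAP 11.3 itself uses age at each visit to derive height, weight and BMI percentiles. The blood-pressure rule names neither.

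Protocol Appendix 2.3 (boys) and Appendix 2.5 (girls) carry the same kind of table: "All blood pressure values listed as follows are 95th percentile for age and height percentile". They cite the same source as SAP Table 8, choose the row by age at last birthday, and include a row for age 6. SAP 17, which lists changes from the protocol, does not mention dropping that row.

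**The concern.** A child who consents shortly before a sixth birthday is eligible and can contribute analysed readings at age 6. What happens to those readings depends on a choice that the SAP does not state:

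- **Age at consent.** The age-5 row applies. A 6-year-old's reading that lies within the protocol's printed age-6 limit can be counted as abnormal.
- **Age at visit.** No row applies. The reading cannot be flagged, but the child stays in the denominator.

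The two readings push the count in opposite directions, and two programmers could reach different counts from the same data. The groups are small. The planned minimum number of girls completing is 2 + 3 = 5, so if only five girls had readings, one reclassified girl would move the female percentage by 1/5 = 20 points.

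**Working it through.** **1. The plan's own durations.** Three full weeks plus Day 9 of Week 4 is 21 + 9 = 30 days (rich). Three full weeks plus Day 8 is 21 + 8 = 29 days (sparse). Both match SAP 2.1.

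**2. Days from consent to last reading.** The last visit falls 29 days (rich) or 28 days (sparse) after Day 1.

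- Consent 32 days before dosing (the maximum): 32 + 29 = 61 and 32 + 28 = 60 days. The allowance of 1 day on the 28 days of dosing can take this to 62.
- Consent 8 days before dosing (the late end of the screening column in the schedule): 8 + 29 = 37 and 8 + 28 = 36 days.

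**3. Expected number who turn 6.** SAP 2.5: "Approximately 24 subjects are expected to be enrolled". I assume 12 rich and 12 sparse, and age at consent uniform over the two-year window (2 × 365.25 = 730.5 days). The documents give no age distribution. A child turns 6 in time with probability days / 730.5.

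- Consent 8 days before dosing: 12 × (37 + 36) / 730.5 = 1.20 children; chance of at least one, 71%.
- Consent 32 days before dosing: 12 × (61 + 60) / 730.5 = 1.99 children; chance of at least one, 87%.

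With a fraction f aged 5 at consent, uniform within that year, the probability is f × days / 365.25:

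- f = 0.25: 0.60 (8 days) to 0.99 (32 days) children.
- f = 0.75: 1.80 (8 days) to 2.98 (32 days) children.

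**4. Gap between the rows.** Protocol age-6 limit minus SAP Table 8 age-5 limit, in mmHg, by height percentile:

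| | 5% | 10% | 25% | 50% | 75% | 90% | 95% |
|---|---|---|---|---|---|---|---|
| Boys systolic | 1 | 1 | 2 | 2 | 1 | 2 | 1 |
| Boys diastolic | 3 | 2 | 2 | 2 | 2 | 2 | 2 |
| Girls systolic | 1 | 2 | 2 | 1 | 2 | 2 | 2 |
| Girls diastolic | 2 | 1 | 2 | 2 | 1 | 2 | 2 |

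That is 1 mmHg in 8 cells, 2 mmHg in 19 and 3 mmHg in 1, of 28. The 3 is 72 − 69, with the SAP's age-5 value. Protocol Appendix 2.3 prints 60 in that cell (boys, age 5, 5th height percentile, diastolic), which would make the gap 72 − 60 = 12. The documents differ there by 69 − 60 = 9 mmHg.

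**5. From birthdays to changed results.** Step 3 counts birthdays, not misclassified children. Under age at consent, a child's result changes only if a post-birthday reading falls in the narrow band between the rows and no other reading flags the child. The documents give no data on how often that happens. For illustration only, if 10% to 20% of the children who turn 6 met both conditions, 0.10 × 1.2 to 0.20 × 2.0 gives about 0.1 to 0.4 children of 24.

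**The case against.** The strongest reply is that Table 8 is complete on the SAP's own terms. SAP 7.1 defines age at consent, every eligible child is then 4 or 5, and where SAP 11.3 wants age at visit it says so. This has force: a reader might infer that 6-year-olds simply have no cut-off, and the documents do not establish that. It does not close the point. The age-at-consent reading still judges a 6-year-old against a younger child's limits under a rule that presents itself as age-specific. That rule also takes a height percentile as an input, and the same section derives height percentiles from age at each visit.

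Three further replies stand.

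- A reader might infer that the SAP contradicts the criterion sites use during treatment. The last-birthday instruction in Appendices 2.3 and 2.5 is written for eligibility at screening and baseline. Protocol 4.4.1.1, the on-treatment rule, refers to age but neither cites the appendices nor repeats the instruction. The two criteria would differ anyway: the protocol uses at or above the 95th percentile, the SAP strictly above.
- A child who turns 6 partway through treatment keeps classifiable readings from before the birthday, so even under age at visit that child is not wholly unclassified.
- Little safety information is at risk. The potentially clinically important blood-pressure limits in SAP Table 6 do not depend on age, all vital signs are listed, and the separate table specifications mentioned in SAP 1, which are not available here, may name the look-up age.

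A reader might extend the point to the pulse limits in SAP Table 7, which also stop at 5 years. The documents give no age-6 pulse limits, and a sentence there would only record a convention.

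**Conclusion.** The point holds as a small gap. Table 8 stops at age 5, the look-up age is not stated, and neither possible choice treats a reading taken at age 6 by an age-6 limit, although the protocol prints one. About 1 to 2 of 24 children would be expected to turn 6 before their last analysed reading if consent ages are uniform; the upper end needs every child to use the full 32-day screening period, and other age mixes give 0.6 to 3.0. The limits differ by 1 to 2 mmHg in 27 of 28 cells.

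A reader might take 1 to 2 of 24 as the number misclassified, or conclude that the abnormal count is biased in a known direction. Neither follows. The figure counts birthdays, the direction depends on an unstated choice, and only children with a post-birthday reading in the band (or with no row) and no other flagged reading are affected. The consequence is a possible misclassification in one descriptive table and its listing. Confidence is high that the row is missing and the look-up age unstated, and lower for the size, which rests on an assumed age distribution.

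**What to change.** In SAP Table 8, add the age-6 rows already printed in Protocol Appendix 2.3 (boys) and Appendix 2.5 (girls). In SAP 11.3, add one sentence saying that age at the visit, as whole years at last birthday, selects the row; this agrees with the growth-percentile rule in the same section. Separately, check the boys' age-5, 5th-height-percentile diastolic value against the cited source and reconcile the two documents (69 in the SAP, 60 in the protocol).

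The cost is two table rows, one sentence and one source check. No data collection changes, and no change to Table 7 is needed.
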